9.5.2 Vital Signs Analysis

Vital signs will be summarized at each protocol scheduled time point, by treatment group at each time point. Where vital signs were captured as continual measures, mean values for that time interval will be recorded. Actual values and actual changes from baseline will be presented.

9.5.3 Prior and Concomitant Medication Analysis

Prior and concomitant medications will be coded using the World Health Organization Drug coding dictionary. Prior and concomitant medications will be grouped by preferred term.

Prior medications are those medications that were stopped prior to commencing the therapeutic intervention. Concomitant medications are medications that are taken at least

once after commencing the therapeutic intervention. Medications stopping on the same day as commencing therapeutic intervention will be considered as concomitant medications.

9.6 Efficacy Analysis

The full presentation of the analysis of efficacy data will be presented in the SAP.

For all subjects, daily reported PCSS scores collected from ClearPlay© mobile application will be utilized to determine the resolution of symptoms. The resolution of symptoms is defined as a symptom-severity score of less than each subject's pre-injury PCSS score for 3 consecutive days. To assess differences in the probability of symptom resolution between graded exercise and passive stretching during the 8 weeks of therapy, both unadjusted and adjusted logistic regression models will be used. The primary outcome of the study will be to confirm or refute the superiority of sub-threshold aerobic exercise versus passive stretching to result in resolution of symptoms following mTBI. Confounders for the adjusted models will include age, gender, anxiety at baseline, history of migraine, cardiovascular fitness, the presence or absence of neurologic findings, and site of enrollment.

The survival probability will be compared using Kaplan-Meier (log rank test) analyses between the 2 treatment arms. Cox proportional hazards regression models will be used to evaluate the differences in time to symptom resolution. Adjusted treatment effects will be estimated in Cox proportional hazards regression models, controlling for the variables listed above. To identify that our randomization strategy was effective, analysis of variance will be used to assess for group-wise differences in age, days since injury to initial visit, initial PCSS score, resting HR, and Δ HR during the BCBT and resting BP and Δ BP during the ice bucket test on Day 1. Non-parametric tests of medians will be used to compare the non-normally distributed variable duration of clinical recovery. Chi-squared tests will be used to assess group-wise differences in gender, history of concussions, and incidence of PPCS.

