Analysis:	
No interim analysis is planned for this study.
 
In general, data will be summarized using descriptive statistics (number of non-missing observations, mean, median, standard deviation, minimum and maximum) or frequency counts and percentages, as appropriate to the type of data.
 
Adverse events and medical history will be coded with Medical Dictionary for Regulatory Activities (MedDRA, the latest version) and concomitant medications are coded with World Health Organization Drug coding Dictionary (latest version).
 
For all subjects, daily reported PCSS scores collected from ClearPlay© mobile application will be utilized to determine the resolution of symptoms. The resolution of symptoms is defined as a symptom-severity score of less than each subject's pre-injury PCSS score for 3 consecutive days. To assess differences in the probability of symptom resolution between graded exercise and passive stretching during the 8 weeks of therapy, both unadjusted and adjusted logistic regression models will be used. The primary outcome of the study will be to confirm or refute the superiority of sub-threshold aerobic exercise versus passive stretching to result in resolution of symptoms following mTBI. Confounders for the adjusted models will include age, gender, anxiety at baseline, history of migraine, cardiovascular fitness, the presence or absence of neurologic findings, and site of enrolment.
 
The survival probability will be compared using Kaplan-Meier (log rank test) analyses between the 2 treatment arms. Cox proportional hazards regression models will be used to evaluate the differences in time to symptom resolution. Adjusted treatment effects will be estimated in Cox proportional hazards regression models, controlling for the variables listed above. To identify that our randomization strategy was effective, analysis of variance will be used to assess for group-wise differences in age, days since injury to initial visit, initial PCSS score, resting heart rate (HR), and ΔHR during the BCBT and resting BP and ΔBP during the ice bucket test on Day 1. Non-parametric tests of medians will be used to compare the non-normally distributed variable duration of clinical recovery. Chi-

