4 STUDY DESIGN AND ENDPOINTS

4.1 Description of the Study Design

This study is designed as an open label study of a therapeutic intervention in subjects who have sustained mTBI. At least 400 subjects aged 14 to 45 inclusive will be enrolled in this study at up to 5 study sites. Subjects will be randomly assigned with a ratio of 1:1 to complete either graded exercise or passive stretching. The study sites will have well-established concussion research programs and referral populations.

The therapeutic intervention is either 20 minutes daily of graded exercise or 20 minutes daily of passive stretching delivered through the ClearPlay© mobile application, downloaded to an Apple i-touch or i-phone device, used in conjunction with a wrist-worn heart rate monitoring device (Waveband®). The sponsor will provide one i-touch or i-phone to each subject to provide them with access to ClearPlay App. This device will also allow subjects to access music for use during exercise or stretching.

Randomization of each subject will occur when the subject has completed all of their Baseline physiologic testing (Ice Bucket Test, ClearHeart© and BCBT) on Day 0.

[figure not shown]
Both the site staff treating subjects and the subjects themselves will be aware of the assigned exercise regimen. Subjects will be stratified based on baseline scores on the PCSS (threshold ≥ 30).

The study consists of 2 study visits and 3 remote telephone visits between the 2 study visits:

- Study Visit 1 (Day 0) – Screening/Baseline visit: within 3 to 14 days of concussion. This visit will serve as a screening visit, to determine eligibility to participate in the study. Eligible subjects will be enrolled, and baseline assessments performed;
- Remote telephone safety assessments – Day 14, Day 28 and Day 42 for safety follow up;
- Study Visit 2 – Follow-up visit: 8 weeks following enrolment (Day 56).

A schematic diagram of the study design is presented in Figure 2.

Figure 2: Study Design

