4.2 Study Objectives and Endpoints

The study objectives and endpoints to be evaluated in this study are presented in Table 1.

Table 1: Study Objectives and Endpoints

Objectives	Endpoints
Primary Objectives	Primary Endpoints
To compare the effects of graded exercise to passive stretching using ClearPlay© on symptomatic recovery rate following mTBI.	
 • Within-subject analysis of change in symptoms over time using the PCSS, comparing short-term ‘survival rates’ between graded exercise and stretching using Kaplan-Meier analyses for days since concussion.
Secondary Objectives	Secondary Endpoints
To compare the safety and tolerability of graded exercise to passive stretching in patients following mTBI.	
 • Adverse events reported from Day 1 through Day 56, including those identified during exercise or passive stretching during the 20 minutes of daily therapy.
To compare symptom resolution following graded exercise compared to passive stretching using ClearPlay© following mTBI.	
 • Within subject analysis of change in the number of subjects who are symptom free at 8 weeks between the 2 groups. Symptom free is defined by subjects having 3 consecutive days of PCSS scores lower than pre-concussion. 
Note: This objective is similar to the primary one, with the primary endpoint being recovery (binary outcome) vs. symptom resolution (continuous variable).
 
 • Determine differences in symptomatic recovery based on gender, baseline scores on the PCSS, baseline athletic fitness (Godin leisure-time exercise questionnaire), the history of injury, a history of migraine, as well as the presence of pre-morbid anxiety.
To compare the effects of graded exercise to passive stretching using ClearPlay© on physiologic recovery rate following mTBI.	
 • Within subject analysis of normalization of physiologic measurements obtained during the BCBT comparing data collected on entry to the study on Day 0 vs. follow up on Day 56 including: 
 - Beat to beat BP; • Determine differences in physiologic recovery based on gender, baseline scores on the PCSS, baseline athletic fitness (Godin leisure-time exercise questionnaire), the history of injury, a history of migraine, as well as the presence of pre-morbid anxiety (BAI; BSI-18; ASI).

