4.3 Appropriateness of Measures

Multiple study sites are required to ensure efficient recruitment of subjects. Medical centers with well-established concussion research programs and referral populations have been selected to ensure subjects have access to appropriately trained and qualified healthcare providers.

The study is randomized to avoid the bias of subject selection for factors known and unknown between the treatment groups.

Randomization will be stratified by site and baseline symptom severity score on the PCSS (threshold $<$ or ≥ 30).

All assessments proposed in this study are considered by ANSwers Neuroscience Pty Ltd and the Investigators to be appropriate and necessary to compare graded exercise to passive stretching in post-mTBI recovery.

The PCSS is a well validated 21-item self-report measure that records symptom severity using a 7-point Likert scale of severity. This widely used symptom checklist ranks concussion symptoms by their severity and persistence.

Assessments used in this study to assess autonomic function include the BCBT, which measures the exacerbation of post-concussive symptoms during 15 minutes of step-wise escalation of cardio-vascular function and the cold pressor test (known as the “ice bucket test”), which has been shown to be diagnostic of mTBI. The BCBT has been validated against the BCTT, which has been shown to be diagnostic of mTBI, and to be predictive of PPCS.

The safety assessments used in this study such as adverse events (AEs) identified during graded exercise or passive stretching during the 20 minutes of daily therapy from Day 1 through Day 56, remote monitoring of vital signs including beat to beat blood pressure (BP), and daily self-reporting of symptoms on the PCSS are considered appropriate for monitoring subject health and well-being in this type of study.

In collaboration with a private diagnostic laboratory (Monogram Biosciences, a Division of Labcorp) who have validated a set of biomarkers reflective of the severity of mTBI assay structural proteins [t-tau, NF-L, GFAP and UCH-L1] and inflammatory cytokines [IL-6, IL-10 and TNF α]) will be analyzed. Blood and saliva samples will be collected at the time of enrollment and at the end of the study.

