6.3.2 Randomization

A computer-generated randomization schedule will be prepared by a statistician prior to the start of the study. Treatment allocation will be made per the randomization list.

After signing the informed consent form/providing assent, subjects will be administered the screening instruments via REDCap Cloud, along with generation of unique subject ID.

Once eligibility has been established, subjects must proceed to complete all Baseline assessments. The Order of Assessment is listed in Section 8.1, Table 4. Randomization of each subject will occur when the subject has completed all of their Baseline physiologic testing on Day 0.

The subject will be assigned a unique randomization number, which will be allocated sequentially based on the pre-determined randomization schedule, and according to their chronological order of inclusion in the study.

Both the unique subject ID and randomization numbers will be used to identify the subject throughout the study period and on all study-related documentation.

Stratification: randomization will be stratified at each enrolment site by the baseline symptom severity score on the PCSS (threshold $<$ or ≥ 30). The baseline PCSS score is reflective of multiple pre-morbid, neurologic, psychologic, and other factors that collectively are likely to significantly impact the presence of PCSS. Rather than stratify the population based on

individual factors, the single composite measure should provide the most efficient and effective starting point for this clinical trial.

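### Baseline PCSS defines the randomisation strata but is missing from the covariates of the adjusted logistic and Cox models

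*Protocol*

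**What the plan says.** **Randomisation.** Section 4.3: "Randomization will be stratified by site and baseline symptom severity score on the PCSS", with a cut at 30. Section 6.3.2 agrees: "randomization will be stratified at each enrolment site by the baseline symptom severity score on the PCSS". Section 4.1 names the PCSS factor alone: "Subjects will be stratified based on baseline scores on the PCSS". Section 6.3.2 explains that baseline PCSS reflects pre-morbid, neurologic, psychologic and other influences, and that stratifying on it is preferred to stratifying on each of them: "the single composite measure should provide the most efficient and effective starting point for this clinical trial".

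**Adjusted analysis.** Section 9.6: "Confounders for the adjusted models will include age, gender, anxiety at baseline, history of migraine, cardiovascular fitness, the presence or absence of neurologic findings", followed by site of enrolment. The synopsis has the same list, ending "the presence or absence of neurologic findings, and site of enrolment". The adjusted Cox models are fitted "controlling for the variables listed above", so they take the same seven covariates.

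**Other uses of baseline PCSS.** Section 9.6 compares initial PCSS between arms by analysis of variance as a check on randomisation. Table 1 in section 4.2 has a secondary endpoint on differences in "recovery based on gender, baseline scores on the PCSS, baseline athletic fitness", injury history, migraine and pre-morbid anxiety.

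**The concern.** An analysis should normally account for the factors that were balanced by design. Stratifying removes chance imbalance on PCSS between arms. If the model then ignores PCSS, its standard error still allows for variation that the design has removed. When PCSS predicts resolution, the test becomes conservative and loses power.

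The protocol itself treats PCSS as prognostic. Section 6.3.2 prefers the composite to the individual factors, whereas section 9.6 adjusts for individual factors and leaves the composite out. Gender, fitness, migraine and anxiety appear both in the Table 1 endpoint and in the section 9.6 list. PCSS appears only in the former, and no reason is given. The balance check in section 9.6 does not adjust the treatment comparison.

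At stake is precision. The omission does not threaten validity.

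**Working it through.** **1. The two lists side by side**

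| Factor | Stratifies randomisation | In the adjusted models |
|---|---|---|
| Site | yes (4.3, 6.3.2) | yes |
| Baseline PCSS, <30 or ≥30 | yes (4.1, 4.3, 6.3.2) | no |
| Age, gender, anxiety, migraine, fitness, neurologic findings | no | yes |

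**2. The protocol's own sample size (section 9.1)**

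Inputs: 80% versus 93%, 90% power, α = 0.05 (taken as two-sided), 1:1 allocation. The mean proportion is 0.865.

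- n = [1.960·√(2·0.865·0.135) + 1.282·√(0.80·0.20 + 0.93·0.07)]² / 0.13² = 143.1 per arm
- With continuity correction: (143.1/4)·[1 + √(1 + 4/(143.1·0.13))]² = 158.1 per arm, or 316.3 in total (318 if each arm is rounded up)

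This matches the stated 316. The calculation uses no covariates, so adding PCSS changes no stated figure.

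**3. Simulation set-up**

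From the protocol: 400 enrolled less 15% attrition = 340 evaluable, 1:1 within strata, 80% control resolution, follow-up to Day 56.

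Assumed, because the protocol is silent: two equal PCSS strata; exponential resolution times; high-PCSS rate equal to r times the low-PCSS rate; the listed covariates represented by one score with correlation ρ to the stratum; two-sided 5% tests.

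Let H be the low-stratum cumulative hazard at Day 56 in the control arm. H solves ½[e^(−H) + e^(−rH)] = 0.20. The planned hazard ratio k solves ½[e^(−kH) + e^(−krH)] = 0.07.

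| r | Control resolution, low / high PCSS | Planned k | Exercise resolution at hazard ratio 1.35 |
|---|---|---|---|
| 0.8 | 83.6% / 76.4% | 1.66 | 88.5% |
| 0.67 | 86.3% / 73.7% | 1.69 | 88.3% |
| 0.5 | 90.6% / 69.4% | 1.76 | 87.8% |
| 0.33 | 95.6% / 64.4% | 1.92 | 86.9% |

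**4. Power at the planned effect** (3,000 runs per case)

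Cox power is 98.9% or more in every case, and adding PCSS gains at most 0.3 points. Logistic power is 94.3–96.5% without PCSS and 94.6–97.3% with it, a gain of at most 1.3 points.

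**5. Power at hazard ratio 1.35** (4,000 runs per case; % without / with PCSS)

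| Model, r | ρ = 0.3 | ρ = 0.5 | ρ = 0.7 | ρ = 0.85 |
|---|---|---|---|---|
| Cox, 0.8 | 70.2 / 70.7 | 71.6 / 72.0 | 71.2 / 71.6 | 71.5 / 71.5 |
| Cox, 0.67 | 69.6 / 71.4 | 70.0 / 71.6 | 70.8 / 71.6 | 71.1 / 72.2 |
| Cox, 0.5 | 65.1 / 70.3 | 65.8 / 70.3 | 69.0 / 72.5 | 70.2 / 71.8 |
| Cox, 0.33 | 57.1 / 71.5 | 59.0 / 71.4 | 63.6 / 71.5 | 65.1 / 70.0 |
| Logistic, 0.8 | 56.7 / 57.0 | 57.5 / 57.9 | 57.7 / 57.7 | 56.6 / 56.4 |
| Logistic, 0.67 | 56.9 / 57.6 | 55.9 / 57.0 | 56.7 / 57.2 | 55.8 / 56.5 |
| Logistic, 0.5 | 50.9 / 53.4 | 49.2 / 50.8 | 51.6 / 53.2 | 51.9 / 52.8 |
| Logistic, 0.33 | 38.7 / 44.8 | 39.9 / 44.1 | 42.5 / 44.8 | 43.4 / 44.5 |

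With 4,000 runs, the simulation standard error of a power near 70% is √(0.7·0.3/4000) = 0.7 points, so differences of a few tenths mean little. A separate simulation at ρ = 0.3 gave Cox powers of 70.5 / 72.6, 65.4 / 70.5 and 58.9 / 73.2 for r = 0.67, 0.5 and 0.33, which is the same pattern.

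**6. Type I error**

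For Cox at r = 0.33, the rates without PCSS are 3.2, 3.2, 4.2 and 5.1% across the four correlations, against 4.8–5.3% with it. The test is conservative unless the other covariates largely stand in for PCSS.

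**7. A simpler cross-check**

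This used a logistic model with treatment only, then treatment plus stratum (340 subjects, 80% versus 93%, 2,000 runs, stratum odds ratio for non-resolution 1 to 8). Without the stratum, type I error was 4.1–4.5% and power 94.6–94.9%. With it, they were 4.1–5.8% and 94.8–95.8%. At odds ratio 8 the mean log-odds ratio for treatment was 1.22 without and 1.33 with the stratum, against a true conditional value of 1.30. The unconditional value is ln(0.93/0.07) − ln(0.80/0.20) = 1.20. The gap therefore reflects conditional versus unconditional odds ratios and is not confounding.

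**The case against.** The strongest reply is that this is SAP detail. Section 9.6 defers the full efficacy analysis to the SAP, and the covariate list is worded so that it can be extended. Section 9.2 asks the SAP to follow the protocol's principal features, and stratification by PCSS is one of them, so a SAP that adds PCSS would comply. All of this is right, and it means the SAP can repair the point. It does not correct the list. The protocol names seven covariates, twice, and an SAP author who implements them as written would leave PCSS out.

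Second, the primary endpoint in Table 1 is a Kaplan-Meier comparison, and an unstratified log-rank test suffers the same loss: 56.2% versus 71.8% stratified at r = 0.33 and hazard ratio 1.35. That figure stands. The difference is that the protocol names the log-rank test without settling whether it is stratified, whereas for the adjusted models it does name the covariates.

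Third, the comparison with Table 1 is only supporting evidence. Injury history is also in that endpoint and absent from section 9.6, while age, neurologic findings and site are in section 9.6 only. The two lists serve different purposes. This is fair, and the case rests on the stratification instead.

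Fourth, the larger gains need a true effect below the planned 13-point difference (6.9 to 8.5 points at hazard ratio 1.35) and a strong PCSS effect. The 14.4-point maximum needs control resolution of about 96% versus 64% between strata and only weak correlation with the other covariates. This also stands, and it limits how much weight those figures can carry.

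**Conclusion.** The point holds. The protocol randomises within PCSS strata, justifies that choice on prognostic grounds, and then specifies adjusted models that keep site and drop PCSS.

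The consequence is modest. Nothing here invalidates the trial, and at the design effect the cost is negligible. If PCSS predicts resolution, which sections 4.2 and 6.3.2 imply but do not quantify, the adjusted tests are mildly conservative and lose some power when the true effect is smaller than planned. The loss shrinks as the listed covariates capture more of PCSS. It is material only for a strong stratum effect. This is a recommended correction because it costs almost nothing; the trial does not depend on it.

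**What to change.** Add baseline PCSS, as the stratum or as the continuous score, to the covariates of the adjusted logistic and Cox models in section 9.6 and in the synopsis.

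Specify the Day 0 value that set the randomisation stratum. Table 4 places a test PCSS entry in the app after randomisation, and section 9.2 defines baseline as the last valid value before dosing, so without this wording the later entry could be taken as baseline.

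The SAP may also stratify the log-rank test by PCSS. That is an option, and its absence from the protocol is not an error.

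The stratum is already recorded for randomisation, so no data collection or sample size changes. Amending the protocol text needs sponsor and HREC approval under section 10.3. Stating the covariate in the SAP before database lock is the cheaper route.

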9 STATISTICAL METHODS

9.1 Determination of Sample Size

The sample size for this study is 400 subjects: 200 to be randomized to graded exercise, and 200 to be randomized to passive stretching. A power calculation was conducted with the minimum difference in probability of symptom recovery of 13%. Specifically, the probability of symptom resolution of passive stretching and graded exercise groups were set to be 80% and 93%, respectively. In order to achieve power of 90% with $\alpha=0.05$, a sample of 316 subjects is required. Allowing the attrition rate of 15%, a total of 363 subjects is required. To be conservative we plan to enroll 400 subjects to appropriately power this study.

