9.8 Handling of Missing Data

For subjects who are withdrawn from the study prior to their completion for any reason, all data compiled up to the point of discontinuation will be used for analysis. All withdrawals will be included in all analyses up to the time of withdrawal.

Subjects who are withdrawn prematurely from study intervention will be included in all analyses regardless of the duration of intervention.

There will be no imputation for missing data, unless otherwise stated.

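### The supportive test of medians on recovery duration ignores right-censoring; applied by default it compares only subjects who resolved, which biases the contrast toward no difference

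*Protocol*

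**What the plan says.** Section 9.6 (Efficacy Analysis) and the synopsis plan several analyses of symptom resolution: logistic regression, a Kaplan-Meier comparison with a log-rank test, Cox models for time to resolution, and a further test: "Non-parametric tests of medians will be used to compare the non-normally distributed variable duration of clinical recovery". The duration is not defined separately, and no rule says what value a subject takes who has not resolved or has withdrawn.

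The event is defined in the same section: "The resolution of symptoms is defined as a symptom-severity score of less than each subject's pre-injury PCSS score for 3 consecutive days". Observation ends at the second visit: "Study Visit 2 – Follow-up visit: 8 weeks following enrolment (Day 56").

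On missing data, Section 9.8 says: "There will be no imputation for missing data, unless otherwise stated". It also keeps withdrawn subjects in all analyses up to the time they leave.

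The design rates are in Section 9.1: "the probability of symptom resolution of passive stretching and graded exercise groups were set to be 80% and 93%, respectively". The same section allows for 15% attrition: "Allowing the attrition rate of 15%, a total of 363 subjects is required".

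The primary endpoint, in the synopsis and Table 1, is the Kaplan-Meier comparison.

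**The concern.** A duration that ends in an event is known only for subjects in whom the event was seen. Everyone else contributes a lower bound. An ordinary test of medians has no place for a lower bound, so under a no-imputation rule a subject without a duration drops out of the comparison.

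The subjects who drop out are the slowest to recover, and there are more of them in the stretching arm. Removing them shortens the apparent duration in that arm more than in the exercise arm. The groups compared are then no longer the randomised groups, and if exercise works, part of its effect disappears from the comparison.

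At stake is a report that shows a clear log-rank difference beside a weak or non-significant test of recovery duration in the same patients, on the trial's central question.

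**Working it through.** **The plan's own figure.** Section 9.1 states: "In order to achieve power of 90% with $\alpha=0.05$, a sample of 316 subjects is required". With p₁ = 0.80, p₂ = 0.93, mean p = 0.865, difference d = 0.13, two-sided 5% and 90% power:

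- n = [1.960·√(2·0.865·0.135) + 1.282·√(0.80·0.20 + 0.93·0.07)]² / 0.13² = 143.1 per arm.
- Continuity-corrected: n/4·[1 + √(1 + 4/(n·d))]² = 158.1 per arm, or 316.3 in total (318 if each arm is rounded up).

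The 316 is therefore reproduced, and 80% and 93% are the rates the plan relies on.

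**Inputs for the check.**

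- Resolved by Day 56: 80% stretching, 93% exercise (Section 9.1, read with the 8-week period in Section 9.6).
- 200 per arm: "The sample size for this study is 400 subjects: 200 to be randomized to graded exercise, and 200 to be randomized to passive stretching".
- Attrition 15% (Section 9.1).
- Shape of the recovery curve: not given in the protocol, so assumed and varied. Time is counted from enrolment.

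**Base case: constant hazard.** The daily rates are −ln(0.20)/56 = 0.02874 and −ln(0.07)/56 = 0.04749, a hazard ratio of 1.65.

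| Comparison | Stretching | Exercise | Gap |
|---|---|---|---|
| All subjects: ln 2 / rate | 24.1 days | 14.6 days | 9.5 days |
| Resolvers only: time at which 40% (half of 80%) and 46.5% (half of 93%) have resolved | −ln(0.60)/0.02874 = 17.8 days | −ln(0.535)/0.04749 = 13.2 days | 4.6 days |

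The share retained is 4.6/9.5 = 0.48.

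**Other curves, each calibrated to 80% and 93% at Day 56.**

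| Assumed curve | Gap, all subjects | Gap, resolvers | Share retained |
|---|---|---|---|
| Weibull, shape 0.5 | 6.6 | 2.5 | 0.39 |
| Weibull, shape 3 | 6.5 | 3.6 | 0.56 |
| Lognormal, sigma 0.5 | 10.0 | 6.8 | 0.68 |
| Lognormal, sigma 1.5 | 9.7 | 5.5 | 0.56 |
| Cure-type, same timing among resolvers in both arms | 2.9 to 4.0 | 0 | 0 |

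The Weibull times are 56·[ln(1−u)/ln(1−p)]^(1/shape) and the lognormal times 56·exp{sigma·[z(u)−z(p)]}. Here p is the arm's Day 56 rate and u is 0.5 for all subjects or p/2 for resolvers.

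**Power, exponential curve, 200 per arm, 1,500 simulated trials.**

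| Analysis | No dropout | 15% random dropout |
|---|---|---|
| Resolvers only, Mood median test | 53% | 52% |
| Resolvers only, Mann-Whitney | 67% | 66% |
| All subjects, non-resolvers ranked last, Mood | 94% | 94% |
| All subjects, non-resolvers ranked last, Mann-Whitney | 99% | 98.5% |
| Log-rank | 99% | 99.6% |

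With dropout, the mean resolver-only gap is 4.4 days. In that column the ranked-last rows also place dropouts last, which is a crude device.

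**The other literal reading.** Section 9.8 could be taken to mean that a withdrawn subject's time on study is entered as the duration, and 56 days for those who stay unresolved. Assume dropout at a constant rate of −ln(0.85)/56 = 0.00290 per day in both arms. The medians become ln 2/(0.02874 + 0.00290) = 21.9 days and ln 2/(0.04749 + 0.00290) = 13.8 days, a gap of 8.1 instead of 9.5. The loss is smaller but in the same direction, and time to withdrawal is counted as recovery.

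**The case against.** The strongest reply is that the protocol nowhere limits this test to resolvers. That is correct: the restriction is what follows when a test without censoring meets a no-imputation rule, and it is not written down. Section 9.8 even says withdrawn subjects stay in all analyses up to withdrawal.

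Nor is it true that a rank or median test can use only resolvers. Both arms are expected to pass 50% resolution, so both medians are identifiable. Ranking unresolved subjects after all resolvers recovers nearly all the power in the table above, and non-parametric methods that handle censoring also exist. This part of the reply stands in full. But the protocol states neither rule, and the reason it gives for the test, non-normality, does not point to either.

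A second reply is that Section 9.6 leaves the full efficacy analysis to the SAP. If the protocol had left the method open, that would settle the matter. It has instead named a method that does not fit the variable, and Section 9.2 has the SAP implement the principal features of the protocol.

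A third is that little depends on this test. It sits among baseline and chi-squared comparisons with no stated decision role. That also stands, and it limits the weight of the point.

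**Conclusion.** The point holds in a limited form. The plan fixes a test that takes no account of censoring for a variable that is censored, and censored more often in one arm (20% against 7% by the design rates). Applied by default, it conditions on recovery. In every model tried this pulled the contrast toward no difference.

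The size depends on an assumed curve: 9.5 days shrinks to about 4.6 under constant hazards, with a retained share from 0 to about 0.68 elsewhere. The calculation also takes dropout as random and equal between arms.

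Three stronger conclusions that a reader might draw are not supported:

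- **That the benefit is halved.** This is close to the exponential result only. The protocol gives no recovery curve.
- **That the primary result is compromised.** The primary Kaplan-Meier comparison and the log-rank and Cox analyses handle censoring and are untouched.
- **That the test could produce a false claim of superiority.** In the models tried the bias works against exercise.

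What remains is a supportive test that may contradict the main analysis for no clinical reason. It should be corrected, but it does not threaten the trial's main conclusion.

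**What to change.** In Section 9.6 and the synopsis, replace the sentence on tests of medians with wording to this effect: the median time to symptom resolution will be estimated by Kaplan-Meier in each arm, with its 95% confidence interval and the between-arm difference. Subjects unresolved at the end of follow-up are censored at Day 56, and withdrawn subjects at withdrawal. The log-rank and Cox analyses already planned are the test of recovery time.

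If the sponsor prefers to keep a rank-based test, the least that is needed is a stated rule for unresolved subjects (for example, ranked after all resolvers) and for withdrawn subjects.

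The cost is a change of wording in two places. No new data are needed, and the Kaplan-Meier, log-rank and Cox analyses are already in the same paragraph.
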